### 2.5.2 Study Period

Subjects will be studied in the Department of Anesthesiology of Washington University-Barnes Jewish Hospital, prior to and during their scheduled hip or knee arthroplasty surgery.

An intravenous catheter will be inserted in an arm for drug administration and in the opposite arm for obtaining blood samples to evaluate the plasma concentrations of ondansetron. The former will be used also for pre/intraoperative fluids and anesthesia drug administration.

At baseline, a 5ml blood sample will be collected for pharmacokinetics and another 5ml sample for genetic analysis.

Ondansetron will be administered in a 16mg single dose as a 15 min intravenous infusion. Although up to 32mg doses of intravenous ondansetron have been used in clinical trials, 16mg is currently the highest FDA-recommended dose for single administration. Two additional 4mg doses of either IV or oral ondansetron will be allowed for postoperative nausea and vomiting treatment in the study subjects, at the discretion of the treating physicians.

A single CSF sample of 4ml will be collected immediately after spinal needle insertion and before administration of spinal anesthesia. This procedure is routinely performed in the holding area, approximately 30 min before the patient enters the operating room (OR) for planned surgical procedure with spinal anesthesia. As only one sample of CSF is obtained from each subject, the timing of the infusion will be scheduled at approximately 30, 60, or 120 min before planned pre-surgical spinal needle insertion. This will allow 3 time-points of CSF samples from the aggregate study cohort. For determination of the above timing, the patients will be randomized in blocks of 3 for infusion timing (approximately 5 subjects per block), to allow even distribution of CSF PK sample time-points.

Six 5mL serial venous blood samples will be obtained from all subjects at 0 (pre-treatment), 15, 30, 60, 120, and 180 min from the beginning of infusion in each patient, regardless of timing for CSF sampling. The samples will be put on ice, centrifuged for 10 min at 5000 rpm. Plasma will be transferred to two 1.5mL vials and stored at -80°C until analysis by HPLC-MS.

The CSF ondansetron pharmacokinetic profile will be constructed using population PK approach, according to the exact time of CSF sampling. Ondansetron concentration in plasma (expected 40-120ng/mL) and CSF (expected 3-12ng/ml) will be determined by HPLC-MS-MS analysis [10].

Ondansetron may cause QT interval prolongation in rare cases; therefore, the subjects' heart rhythm will be monitored throughout the infusion and for approximately 30 min after the end of infusion using standard 4 lead monitors in the holding area. No changes will be made to the routine intraoperative management and hemodynamic physiological monitoring, with the exclusion of the PK blood sampling period.

The DNA isolation and genotyping will include analysis of single nucleotide polymorphisms (SNPs) in OCT1 and P-glycoprotein transporters. We will genotype for the following five P-glycoprotein (ABCB1) SNPs: C3435T, T-129C, G1199A, C1236T, G2677T [11-14], and for five OCT1 (SLC22A1) SNPs: R61C, C88R, G401S, M420del, or G456R that have reported to affect ondansetron pharmacokinetics or clinical antiemetic effect. The genotyping will be performed at Washington University Genome Technology Access Center. The whole blood samples will be extracted using the QIAamp DNA mini Blood kit (QIAGEN). The DNA will be quantified and quality controlled using nanodrop and gel readings. The SNPs will be interrogated using Taqman probes (Applied Biosystems). Each SNP will have its own 20µl reaction well with a final

concentration of 1X Taqman probe mix, 1X Taqman PCR master mix, and 20-40ng of DNA. The samples will be cycled and analyzed on CFX96 Real-time PCR Detection System (Bio-Rad). The collected blood and DNA samples will be de-identified and coded to ensure patient confidentiality and HIPPA compliance.

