## 1. SYNOPSIS

Study Title	Investigation of cerebrospinal fluid (CSF) pharmacokinetics of ondansetron
Brief Title	CSF PK of ondansetron
Objective	To determine human cerebrospinal fluid (CSF) and plasma pharmacokinetic parameters of 5HT3R antagonist ondansetron after intravenous administration.
Hypothesis	Approaches to enhance CNS penetration of ondansetron might be useful for obtaining analgesic effect with 5HT3R antagonists in neuropathic pain.
Study Period	Planned enrollment duration: Approximately 3 months Planned study duration: One (4-hour) study day per subject, on the day of knee/hip arthroplasty surgery.
Number of Subjects	15 evaluable subjects having elective hip or knee arthroplasty with spinal anesthesia from up to 30 consented subjects.
Study Treatment	Single intravenous 15-min infusion of 16mg ondansetron.
Study Design	Prospective, open-label, pharmacokinetic pilot study.
Inclusion and Exclusion Criteria	
Inclusion criteria:
 
 
1. Age between 18 and 70 years old;
 
2. Patients planned to undergo hip or knee arthroplasty with spinal anesthesia;
 
3. Ability to provide informed consent
 
 
Exclusion criteria:
 
 
4. Not giving consent to participate in the study;
 
5. Patients with history of or current hepatic or renal insufficiency;
 
6. Patients with <math>BMI \geq 33</math>;
 
7. Patients with heart failure or active arrhythmias;
 
8. Patients with severe systemic disease that is a constant threat to life;
 
9. Contraindication or allergy to ondansetron;
 
10. Pregnancy or lactation.
 
11. Prisoners
 

Measurements	
Ondansetron CSF and plasma Pharmacokinetics:
 
 
1. A single 4-mL CSF sample per subject.
 
2. Serial blood sampling at 0 (pre-infusion), 15, 30, 60, 120, and 180 min after ondansetron administration.
 
 
Genotyping: A blood sample will be obtained at baseline for determining the following single nucleotide polymorphisms (SNPs) as confounders of ondansetron PK parameters:
 
 
1. ABCB1 gene (p-Glycoprotein transporter): C3435T, G2677T, T-129C, G1199A, C1236T.
 

	2. In SLC22A1 gene (OCT1 transporter): R61C, C88R, G401S, M420del, G456R.

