### **2.5.4 Observations and Measurements**

#### **2.5.4.1 Primary Outcome Measures**

##### Primary outcome:

Plasma and CSF concentrations of ondansetron, and CSF to plasma concentration ratio.

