#### **2.5.4.3 Pharmacokinetic data analysis:**

Individual plasma concentration-time data will be analyzed using non-compartmental methods. The following PK parameters will be calculated and compared between subjects with different transporter expression level: volume of distribution, systemic clearance, the elimination half-life, and the total area under the concentration-time curve. In addition, a compartmental population-based pharmacokinetic model will be constructed, which will evaluate inter-subject variability in pharmacokinetic parameters. Preliminary assessment of published data indicates that the systemic disposition of ondansetron follows two-compartment model with linear elimination following intravenous administration in humans.

The population model will include a “CSF distribution compartment”, which will allow for the estimation of the partition coefficient between the plasma and CSF. The effect of transporter expression level phenotypes on individual pharmacokinetic parameters will be evaluated using a standard covariate analysis. Utilization of population approach will allow for estimation of population mean and individual patients parameters. This pharmacokinetic methodology is especially useful for analysis of sparse data (i.e., a single CSF sample from each patient).

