## **3.0 Management of Intercurrent Events**

### **3.1 Adverse Experiences**

The investigators will closely monitor subjects for evidence of ondansetron adverse events. All adverse events will be reported and followed until satisfactory resolution. The description of the adverse experience will include the time of onset, duration, severity, etiology, relationship to the study drug (none, unlikely, possible, probable, highly probable), and any treatment required. The clinicians will manage any postoperative event related to the spinal anesthesia as standard of care.

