### **4.2 Sources of Materials**

Subjects will be recruited from Washington University Orthopedics and the Center for Perioperative Assessment and Planning (CPAP), as well as from BJH Surgery registration and the preoperative holding area.

Data on comorbidities and concomitant medication use are provided by subjects. Specimens include blood obtained for transporter genotyping and for determining ondansetron plasma concentration. CSF samples are obtained for determining ondansetron CSF concentration.

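### Does the plan need a written rule for extra ondansetron given before the 180-minute plasma sample?

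*Combined protocol and SAP*

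**What the plan says.** The Synopsis defines the treatment as "Single intravenous 15-min infusion of 16mg ondansetron". Section 2.5.2 then adds that "Two additional 4mg doses of either IV or oral ondansetron will be allowed for postoperative nausea and vomiting treatment in the study subjects", at the treating physicians' discretion. The same section takes plasma "at 0 (pre-treatment), 15, 30, 60, 120, and 180 min from the beginning of infusion in each patient" and describes subjects as studied "prior to and during their scheduled hip or knee arthroplasty surgery".

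The primary outcome (section 2.5.4.1) is "Plasma and CSF concentrations of ondansetron, and CSF to plasma concentration ratio". Section 2.5.4.3 plans an individual non-compartmental analysis (NCA) giving volume, clearance, half-life and total AUC, and a population model with a CSF compartment. On the NCA it says: "The following PK parameters will be calculated and compared between subjects with different transporter expression level".

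Two places touch on recording. Section 3.1 asks that adverse event descriptions include "relationship to the study drug (none, unlikely, possible, probable, highly probable), and any treatment required". Section 4.2 says: "Data on comorbidities and concomitant medication use are provided by subjects". Neither asks for the dose, route and clock time of extra ondansetron for pharmacokinetic use.

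**The concern.** The analysis is written for one 16 mg dose, yet the protocol permits up to 8 mg more of the same drug and does not place it relative to the last plasma sample. If a subject received some of it before 180 min and the analyst did not know, the late concentrations would not be single-dose values. The terminal slope would flatten, the extrapolated AUC would grow, and clearance would come out too low.

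With 15 subjects split by transporter genotype, some groups could be very small, and one badly wrong clearance could pass for a genotype effect. The risk would also fall unevenly across the CSF-timing groups, because the shorter the lead time before the spinal needle, the more of the sampling window falls after surgery starts.

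**Working it through.** **Can the event occur?** Section 2.5.2 schedules the infusion about 30, 60 or 120 min before spinal needle insertion, which is itself about 30 min before operating-room entry. Counted from the start of infusion:

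| Group | Operating-room entry | Time from entry to 180-min sample |
|---|---|---|
| 30 min | 30 + 30 = 60 min | 180 − 60 = 120 min |
| 60 min | 60 + 30 = 90 min | 180 − 90 = 90 min |
| 120 min | 120 + 30 = 150 min | 180 − 150 = 30 min |

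Surgery must end, nausea arise and a dose be given within the last column. That is plausible mainly in the 30-min group (about 5 subjects), possibly in the 60-min group. The protocol gives no duration of surgery, so the frequency is unknown and may be zero. The CSF sample is drawn before spinal anaesthesia and so before any postoperative dose.

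**How large would it be?** The protocol gives no clearance, volume, half-life or slope rule, so there is no stated figure to reproduce. Section 2.5.2 expects plasma levels of 40-120 ng/mL without times. *Assumption:* 120 ng/mL at 15 min, 40 ng/mL at 180 min, one compartment.

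- k = ln(120/40) / 2.75 h = 0.3995 per h; V = 126.9 L; CL = k × V = 50.7 L/h.
- Without an extra dose: AUC(0-180) = 215.3 and tail = 40/0.3995 = 100.1 ng·h/mL. NCA CL = 16 mg / 315.4 ng·h/mL = 50.7 L/h.
- Add 4 mg IV over 2 min at 150 min. It contributes 26.0 ng/mL at 180 min, so C(180) = 40 + 26.0 = 66.0 ng/mL (+65%), above the 120-min value of 59.6.
- Four-point slope: 0.213 per h. AUC(0-180) = 228.9, tail = 310.0, CL = 16 mg / 538.9 ng·h/mL = 29.7 L/h (−41%). Three points give 23.8 L/h (−53%), five give 31.8 L/h (−37%).

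Over doses at 120 to 175 min, the fall is 34% to 48% (four points), 43% to 63% (three) and 31% to 43% (five). Uncounted dose alone, with AUC captured fully, would give 16/20 − 1 = −20%; the rest comes from the flattened slope.

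**How firm is that?**

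- Nine two-compartment sets with the same two concentrations and the dose at 150 min give −43% to −49% (four points) and −34% to −36% (five).
- In a wider two-compartment grid (25, 40 or 60 ng/mL at 180 min, several half-lives, slope rules and dose times; 3168 cases), 88% show a fall of at least one third. The smallest fall is 7%, and in some cases the slope cannot be estimated.
- An oral 4 mg dose at 120 to 150 min (assumed bioavailability 0.5-0.7, absorption rate 0.75-3 per h) gives −7% to −26% with four points.
- One affected subject moves the mean of 15 by 41.5%/15 = 2.8%.

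**Does ordinary handling cure it?** In simulated 15-subject two-compartment fits (plasma only, started at the true values), omitting the dose shifted the affected subject's median model clearance by −33% to −38%. Entering it left +0.2% to +0.5%, and entering it 15 min too early left −3.5% to −6.8%. For NCA, dropping the 180-min value in the one-compartment example leaves AUC(0-120) = 15.0 + (120 − 59.64)/0.3995 = 166.1 and tail = 59.64/0.3995 = 149.3. CL = 16 mg / 315.4 ng·h/mL = 50.7 L/h, the value without the extra dose.

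**The case for a change.** The best case for a change is that the omission is real and cheap to close. No section ties the extra doses to the sampling window, and a dose time not captured on the day may be hard to recover. The text also leaves room for wider exposure. Section 2.5.6 says ondansetron is routine in these patients for prophylaxis as well as treatment. Section 2.5.2 leaves intraoperative management as usual, with an exception for the PK sampling period whose meaning is unclear. If prophylactic doses were given during surgery, the event would no longer be rare.

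Part of this stands: the rule is unwritten, and the exception can be read in more than one way. But the only extra doses the protocol expressly allows are postoperative. One reading of the exception would limit intraoperative ondansetron during sampling. Section 3.4 has research nurses monitoring throughout the study session, and section 3.1 records treatment given for an adverse event. The large percentages apply only if the analyst treats a known second dose as if it had not happened, and nothing in section 2.5.4.3 says that only one dose may be entered.

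Nor is the unaffected NCA a clean reference. Because sampling stops at 180 min, four-point clearance in the nine two-compartment sets is already 8% to 155% above the true value with no extra dose. A more elaborate rule, such as moving the whole transporter comparison to model estimates once one subject is affected, would be a data-triggered switch with problems of its own: in one simulated set those estimates ranged from −38% to +95% of truth (10th to 90th percentile).

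**Conclusion.** No change to the plan is needed. This is a missing detail about an event that may not occur, and a pharmacokinetic analyst would fill it sensibly by entering the dose in the population model and keeping later samples out of that subject's single-dose NCA and summaries.

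If the dose were ignored, that subject's total-AUC clearance would be too low by roughly 30% to 60% for one IV dose in most settings examined, and 7% to 26% for one oral dose. These figures rest on assumed kinetics anchored only to the protocol's expected concentration range. In this pilot and feasibility study NCA clearance is a secondary outcome. Within the primary outcome, only the late plasma concentrations could be touched.

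The conclusion assumes that extra doses are postoperative, as section 2.5.2 words them, and that their times can be obtained from the clinical record. It takes no position on whether or when extra ondansetron should be given.

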## 2.5 Design and Procedures

### 2.5.1 Study Design and Methodology

The potential subjects will be recruited from the Washington University / Barnes Jewish Hospital center for perioperative assessment and planning (CPAP) and the Washington University Orthopedics outpatient clinics, before their scheduled visit for elective knee or hip arthroplasty. Subjects may also be recruited from BJH Surgery Registration and the preoperative holding area on the day of surgery. Subjects who are potential candidates for the study will be provided with written and oral description of the study procedures, benefits, and potential risks. They will be given the opportunity to ask questions regarding the study. Informed consent will take place at Washington University/Barnes-Jewish Hospital medical center campus.

If agreeing to participate in the study, each subject will sign the informed consent document. Each subject who qualifies for entry into the study on the basis of inclusion/exclusion criteria and completion of informed consent will be assigned the next available patient number. This indicates enrollment in the study. In subjects with a history of or suspected renal or hepatic disorder, blood tests will be ordered following consent and reviewed prior to study participation for plasma creatinine, Alanine aminotransferase (ALT), Aspartate aminotransferase (AST) and albumin. Subjects with moderate or severe renal or hepatic failure will be excluded from the study at the discretion of the PI. Subjects with any history of cardiac arrhythmias will undergo 12 lead ECG to rule out QTc interval >450ms and will be excluded from the study.

Patients' demographic data will be recorded; height and weight will be measured for calculating BMI. Subjects who drop out of the study prior to completing the study will be replaced by using the next available subject number.

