### **3.2 Premature Discontinuation**

If a subject withdraws from the study, the subject will be replaced in order to provide the required number of evaluable subjects. Subjects will be withdrawn if the investigator decides that discontinuation is in the best interest of the subject, or the subject requests withdrawal from the study.

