#### **4.3 Recruitment and Informed Consent**

Participants will be recruited primarily through Washington University Orthopedics and the Center for Perioperative Assessment and Planning (CPAP).

Two primary recruitment mechanisms will be utilized:

1. Participants will be referred from Washington University Orthopedics by the corresponding physicians. Interested subjects will contact the investigators.
2. A weekly list of patients scheduled for CPAP visit before knee or hip arthroplasty will be generated from SIS system. The potential subjects will be approached by the study coordinator for inclusion consideration.

Subjects may also be consented in the surgery registration area and the preoperative holding area.

Subjects will be given verbal (initially) and then written descriptions of the study aims, procedures, risks, and benefits, and will be required to give written informed consent. A member of the investigative team provides all study descriptions, informed consent, and answers all questions.

Subjects are informed verbally and in writing that participation is voluntary and they may refuse to participate and may withdraw from the study at any time without penalty. Subjects that participate, but do not complete all study procedures because their surgery is cancelled or rescheduled by their treating physician may re-consent to participate and be re-enrolled as long as there has been a minimum of 48 hours between the last study procedure and the re-consent event.

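### Should a replacement or re-enrolled subject have to take the CSF sampling time of the subject who was lost?

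*Combined protocol and SAP*

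**What the plan says.** Each subject gives one CSF sample. Section 2.5.2 schedules the infusion about 30, 60 or 120 min before spinal needle insertion, with subjects "randomized in blocks of 3 for infusion timing (approximately 5 subjects per block), to allow even distribution of CSF PK sample time-points". The synopsis sets 15 evaluable subjects from up to 30 consented.

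Three rules govern lost subjects:

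- Section 2.5.1: "Subjects who drop out of the study prior to completing the study will be replaced by using the next available subject number".
- Section 3.2: "If a subject withdraws from the study, the subject will be replaced in order to provide the required number of evaluable subjects".
- Section 4.3: subjects who do not complete the procedures "because their surgery is cancelled or rescheduled by their treating physician may re-consent to participate and be re-enrolled", after at least 48 hours.

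None of these mentions the CSF time. The documents also do not say when timing is randomised, or whether it is tied to the subject number. For the analysis, 2.5.2 builds the CSF profile by population PK "according to the exact time of CSF sampling", and 2.5.4.3 says of that approach: "This pharmacokinetic methodology is especially useful for analysis of sparse data".

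**The concern.** Blocking balances the subjects who are assigned, whereas the CSF analysis needs a spread among those who are evaluable. If a lost 120-min subject is replaced by the next number on the list, that number may carry a different time. With about 15 CSF samples in all, a few such losses could thin one time point, and the CSF/plasma ratio is part of the primary outcome.

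The 120-min group is the one to worry about, because it is the only late time. Spinal needle insertion takes place "approximately 30 min before the patient enters the operating room", so a 120-min subject starts the infusion about 120 + 30 = 150 min before the operating room, against 30 + 30 = 60 min for a 30-min subject. That leaves more time for the surgery list to change. Section 2.5.1 adds: "Subjects may also be recruited from BJH Surgery Registration and the preoperative holding area on the day of surgery". Such recruits may have little time left for a 120-min slot.

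The sentence on blocks also looks wrong by itself, since a block of 3 cannot hold about 5 subjects.

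**Working it through.** **The plan's own figures.** 15 evaluable / 3 CSF times = 5 per time, which matches the stated figure of about 5. So the 5 is the count per CSF time and the 3 is either the block size or the number of timing groups. The slip is clerical. Loss after consent is at most 1 − 15/30 = 50%. This is an upper bound, since loss before timing is assigned does no harm.

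**Assumptions, none of them in the documents.** Timing follows subject number in permuted blocks of 3. Loss occurs after assignment, and each loss is replaced by the next number until 15 are evaluable. The CSF/plasma ratio at time t is Kp(1 − exp(−kt)), with 50% CV (log-scale variance ln 1.25 = 0.223) and an equilibration half-life of 15, 30, 60 or 120 min.

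**Formula.** The gradient for (log Kp, log k) is (1, g), with g = kt·exp(−kt)/(1 − exp(−kt)). With n subjects at each time and N = 15,

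Var(log Kp) = 0.223 × Σng² / (N·Σng² − (Σng)²).

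**One case by hand, half-life 60 min.** g = 0.837, 0.693 and 0.462 at 30, 60 and 120 min.

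- 5/5/5: Σng² = 6.970, Σng = 9.960, variance 0.290, SE 0.539.
- 6/5/4 (one fewer at 120 min): Σng² = 7.457, Σng = 10.334, variance 0.329, SE 0.574, ratio 1.065.
- 4/5/6 (one more at 120 min): Σng² = 6.484, Σng = 9.585, variance 0.269, SE 0.519, ratio 0.962.

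The two opposite drifts average (1.065 + 0.962)/2 = 1.014. Chance imbalance therefore costs little on average, and 5/5/5 is not the most precise split in this model. Over the four half-lives, 4/5/6 lowers the SE by 2 to 6%.

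**Equal loss at all three times (simulation, relative to 5/5/5).**

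| Loss | Mean rise in SE(log Kp) | Trials with rise above 10% | Trials at 5/5/5 or 6/5/4 in any order | Mean subjects needed, 15/(1 − loss) |
|---|---|---|---|---|
| 10% | 0.4–0.7% | 2% | 94% | 16.7 |
| 20% | 0.7–1.2% | 6% | 83% | 18.8 |
| 30% | 1.0–1.7% | 10% | 71% | 21.4 |
| 40% | 1.3–2.3% | 14% | 61% | 25.0 |
| 50% | 1.6–2.9% | 17% | 53% | 30.0 |

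In 28 to 45% of trials the uneven split is slightly more precise than 5/5/5. The largest mean rise, 2.9%, is worth about 15 × (1 − 1/1.029²) = 0.8 of a subject.

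**Unequal loss (30/60/120 min, illustrative rates).**

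| Loss | Mean change in SE(log Kp) | Trials with 3 or fewer samples at 120 min |
|---|---|---|
| 10/10/20% | +3 to +4% | 9% |
| 10/10/30% | +6 to +8% | 22% |
| 10/20/40% | +9 to +11% | 34% |
| 30/10/10% | −3 to +1% | below 1% |

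The worst of these, 11.3%, is worth about 15 × (1 − 1/1.113²) = 2.9 subjects.

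**Sensitivity to the model.** With a 15-min infusion, a falling plasma level and a CSF compartment (36 assumed settings), the mean rises are 0.2–2.7% for equal loss, 2–9% for 10/10/30% and 4–13% for 10/20/40%. The conclusion is the same.

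**What same-time replacement would cost.** With equal loss it needs the same number of subjects on average. At 10/10/30% it needs 18.3 against 18.0, and at 10/20/40% 20.1 against 19.6. At an extreme 30/50/70% it needs 33.9 against 30.0, above the limit of 30 consents, so it would not secure the even spread where loss is worst.

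**The case for a change.** The strongest case for a change is that the plan states an aim, an even spread of CSF times, and its replacement rules do not protect it. The edit would be short and nearly free. An average also hides the tail: even with equal loss, some CSF time ends with 3 or fewer samples in 5% of trials at 10% loss and 37% at 50% loss. Loss concentrated at 120 min is plausible, and 4.3 itself foresees cancelled and rescheduled surgery.

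The gap in wording stands: no rule mentions the CSF time. The rest is weaker. A list change that only delays the spinal moves the sampling time without losing the sample, and the model takes the time as it was. Only cancellation or a move to another day loses the sample, and 4.3 then allows re-enrolment. The unequal loss rates are assumed throughout. The sentence in 2.5.2 can also be read as three timing groups of about 5 each. On that reading the quota per time is already set, and the rule in 3.2 can be taken as refilling it.

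**Conclusion.** No change to the plan is needed. The rules leave a detail open that staff can fill sensibly, since 2.5.2 gives both the aim and the target of about 5 per CSF time, and nothing prevents them from filling open times first. If they do not, and if timing follows subject number with loss after assignment, the average cost under equal loss is a 0.4 to 2.9% larger standard error for log Kp, worth less than one subject. A cost of 6 to 11% needs loss concentrated at 120 min, at rates the documents do not give.

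There is no bias from uneven counts, because exact sampling times are modelled. This assumes that loss is unrelated to a subject's CSF uptake, which is reasonable when the cause is the surgery list. The study is a feasibility pilot whose size rests on precedent (2.5.5), so no precision target would be missed. The block wording is a clerical slip with a clear meaning. The size figures rest on the assumed uptake model, 50% CV and half-lives of 15 to 120 min.
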